10.15 Duration of Hospitalization

The duration of hospitalization will be calculated as

$$\text{Duration (days)} = \text{End date of hospitalization} - \text{Start date of hospitalization} + 1$$

The duration of multiple hospitalizations, including re-hospitalizations due to COVID-19 in the period will be summed together to derive the overall duration of hospitalization. For subjects who were hospitalized on the date of first dose of IMP, the date of first dose of IMP will be used as the start date. If a subject is still hospitalized at the end of the 60-day period the date of trial completion will be used.

For subjects who die they will be considered hospitalized from date of death through Day 60. For subjects who discontinue the trial prior to discharge from hospital, the number of days of hospitalization will be set to 60 days (it will be assume they did not discharge from hospital). If a subject discontinues the trial following discharge for reasons other than death and there is no further hospitalization data available then for the purpose of the analysis the subject will be considered to be not re-admitted in the period and no additional imputed days will be added to the number of days recorded on the available assessments.

An additional sensitivity analysis will be performed where missing data will be imputed as per Section 10.19.1, such that subjects who are early withdrawals will have data imputed following withdrawal and

where all re-hospitalizations are considered as COVID-19 related regardless of the investigator indicated cause.

10.16 Duration of ICU Stay

The duration of ICU stay will be calculated as

$$\text{Duration (days)} = \text{End date of ICU stay} - \text{Start date of ICU stay} + 1$$

The duration of multiple ICU stays in the period will be summed together to derive the overall duration of ICU stay. If a subject dies or discontinues prior to the end of the ICU stay or the subject died and had no ICU stay, the subject will be considered in the ICU from the date of death/discontinuation through Day 60. For subjects who discontinue the trial in hospital but not in ICU or discontinue following discharge they will not have any imputed additional days added to the number of days recorded on the available assessments. If the start date of the ICU stay is prior to treatment start, the treatment start date will be used as the ICU start date in the above derivation. For subjects with no ICU stay a value of 0 days will be used in the analysis. Note that ICU stays associated with re-admission for non-COVID reasons should not contribute to the duration.

10.17 Duration of Invasive Ventilation or ECMO

The duration of invasive ventilation or ECMO use will be calculated as

$$\text{Duration (days)} = \text{End date of use} - \text{Start date of use} + 1$$

The duration of multiple invasive ventilation or ECMO use will be summed in the period to derive the overall duration. For subjects who die they will be considered on invasive ventilation or ECMO from date of death through Day 60. Subjects who discontinue the trial prior to discharge from hospital with last ordinal scale assessment of 7 will be considered on invasive ventilation or ECMO from date of discontinuation through Day 60. Subjects who discontinue the trial in hospital with last known status on the 8-point ordinal scale of ≤ 6 or subjects who discontinue following discharge will be considered not on invasive ventilation or ECMO through Day 60 and will have no additional days added to the number of days recorded on the available assessments. For subjects with no invasive ventilation/ECMO use a value of 0 days will be used in the analysis.

10.18 Data handling for SpO₂ and FiO₂

SpO₂ will be collected on the Oxygen saturation form daily for hospitalized subjects. SpO₂ will be collected twice at a visit and the average of the two assessments will be used as the value in the analysis. If only one assessment is available at a visit this will be the value used in the analysis. Discharged subjects will not have site assessments performed. Day 15 will be the only time point examined for this endpoint.

Subjects on low flow oxygen, high flow device or mechanical ventilation will use the value of FiO₂ as entered on the eCRF by the investigator. Subjects on room air will have a value of 21% for FiO₂ assigned. Subjects on ECMO will not have FiO₂ collected. In this case in the calculation of the SpO₂/FiO₂ ratio the last observation for this ratio prior to the subject moving to ECMO ventilation will be used. If the value of FiO₂ is missing, but information on the type of device and oxygen flow is collected, Appendix 3 will be used to assign a value of FiO₂ to use in the calculation of the SpO₂/FiO₂ ratio.

At a visit a subject may have a SpO₂ reading on an oxygen device and another reading at the same visit on room air. In this case the ratio SpO₂/FiO₂ will be calculated using the on room air value only for SpO₂ and a value of 21% for FiO₂.

10.19 Missing Data

In general, missing safety data will not be imputed. However, safety assessments in the form of <x (i.e. below the lower limit of quantification) or >x (i.e. above the upper limit of quantification) will be imputed as x in the calculation of summary statistics but displayed as <x or >x in the listings. Missing FiO₂ values will be imputed as per Appendix 3.

In all efficacy analysis subjects who die will always be treated as the worst case following the date of death. For endpoints where multiple imputation will not be implemented, subjects who discontinue the trial early will be assessed in the analysis based on their last known status as discussed in Sections 10.15, 10.16 and 10.17. Other missing data will be imputed using multiple imputation as outlined below.

10.19.1 Multiple Imputation

Missing ordinal scale data at scheduled time points will be imputed using multiple imputation. Multiple imputation relies on the assumption of data being missing at random (MAR) i.e. the missingness can be explained by the observed data and missing data does not depend on unobserved data after accounting for observed factors. Subjects will only have missing data imputed for post-baseline scheduled visits (Day 2 to Day 29, Day 60).

The following steps will be used to impute the missing data. Prior to the missing data imputation all observed 8-point ordinal scale data will be re-mapped per Table 3 to ensure discharged subjects with supplemental oxygen use are treated as clinically worse than discharged subjects with no oxygen use. This will also ensure information on at home oxygen use is explicitly contained in the ordinal scale score. The value of the adjusted 8-point ordinal scale to use in the analysis for all days following discharge will be assigned as per Section 10.10. On the day of discharge, the following rules will be used to assign a value of the adjusted ordinal scale:

- If a subject has a scheduled visit with an ordinal scale value other than 2, this value will be used in the analysis for the day of discharge.
- If a subject has a missing assessment or a value of 2 is recorded as the scheduled assessment, a subject will be assigned a value of 1 or 2 on the adjusted 8-point ordinal scale on the day of discharge as outlined in Section 10.10.

If a subject has an ordinal scale value of 8 at any visit or the subject has a date of death, records on or following date of death will be handled as follows in the analysis:

- All days following day of death will be set to 8.
- For the day of death, if the subject has a non-missing value on the ordinal scale that is not a value of 8 this will be the value used in the analysis.
- If a subject has a missing value on the day of death the value of 8 will be used.

Subjects who die will be removed from the Imputation in step 2. Only subjects who have not died will have their data imputed. Following the imputation, data for subjects who died will be included in all imputed datasets as observed.

A random seed of 2188 will be used for all imputation in this analysis.

1. Prior to the imputation, missing data pattern for ordinal scale data will be explored. If the pattern of missing data is non-monotone (for example intermediate missing data due to missing follow-up visits), intermittent missing ordinal scores will be imputed under a missing at random (MAR) model for missing data using a Markov chain Monte Carlo (MCMC) method of imputation to ensure data follows a monotone missing data pattern i.e. if data is missing at Day X it will be missing for all subsequent time points. The 8-point ordinal scale will be imputed using PROC MI with the MCMC impute=MONOTONE specification and specifying the variables in order of scheduled visits (Day 2 up to Day 29, Day 60), in order to partially impute intermediate missing values only.

A minimum value of 1 and maximum value of 7 will be specified to ensure values are not outside the range of possible ordinal scale scores. Values will be rounded to the nearest whole number and 1,000 burning iterations will be used. Graphical tools will be used to check for any signs of non-convergence and if non-convergence is an issue, the number of burn-in iterations should be increased.

If the model does not converge as values within the minimum/maximum range can not be imputed, the minimum and maximum criteria will be removed. Subjects which have values outside the minimum and maximum will be reviewed and the following process will be followed to obtain convergence:

- For values below the minimum and above the maximum the largest absolute deviation from the minimum/maximum will be determined. The subject with the largest absolute deviation for the non-monotone data will have the data point assigned using last observation carried forward (LOCF)
- The MCMC will be re-run (with minimum/maximum specified). If setting the minimum/maximum results in convergence these results will be used in Step 2 of the MI process. Otherwise the process will be repeated until setting minimum/maximum results in convergence or no further subjects with unrealistic data can have non-monotone data imputed with LOCF.
- If after these steps are applied and there is no convergence, the MCMC will not be used and LOCF will be used for all subjects to impute their non-monotone data.

This step will only be performed if missing data does not follow a monotone missing data pattern. This step assumes data is multivariate normally distributed which will not be the case for ordinal data. However, as the number of non-monotone data is expected to be small, the overall impact of this partial imputation step on the analysis at the time point of interest will be small. Subjects who died will be included in this step. Further it is accepted that values of 1 and 2 may be imputed for non-monotone data prior to the observed date of discharge. No adjustments will be made for this as these values are theoretically possible.

2. Missing 8 point ordinal scale data at time point X will be imputed for subjects who did not die using a logistic regression model with the factors of
 - a. Treatment group
 - b. Actual baseline ordinal scale score
 - c. Region (Pooled)
 - d. Age (will not be included in the CLASS statement in the PROC MI)
 - e. Post-baseline daily values of adjusted 8-point ordinal scale up to time point X

Values will be restricted to a minimum value of 1 and a maximum value of 7, as values of 8 will not be present in the data per the previous rules outlined. It is noted that at a time point only values of the ordinal scale recorded at the time point will be possible imputed values. Imputed values may be inconsistent with other data, for example it is possible that an imputed value will be 3 (Hospitalized, not requiring supplemental oxygen - no longer requires ongoing medical care) even if supplemental oxygen is documented on the concomitant medication page.

The number of imputations will depend on the percentage of missing data to be imputed and will range from a minimum of 20 to a maximum of 50. The number of imputations will increase from the minimum of 20 to the maximum of 50 according to the formula:

$$\text{Number of imputations} = 20 + 1.5 * (m)$$

where m is the proportion of missing data, expressed as a percentage. The smallest integer that is greater than or equal to the number will be used (note this will be based on missing data present following step 1 and will not include subjects who died in the calculation)

By default SAS PROC MI, uses the option "LIKELIHOOD=NOAUGMENT" for the computation of maximum likelihood estimates. If the maximum likelihood parameter estimates do not exist or any warning results from this option, the option "LIKELIHOOD=AUGMENT" will be used to get the maximum likelihood estimates.

3. Imputed values from each of the imputed datasets in step 2, data for subjects who died and non-missing data will be used to calculate the responder status for a subject at a time point for the following endpoints:

Sensitivity Analysis for Time to Sustained Hospital Discharge

For each of the imputed datasets, the time to sustained hospital discharge will be derived. If a subject has an observed or imputed score of ≤ 2 on the ordinal scale where for all subsequent visits the observed or imputed score stays at or below 2 the earliest occurrence will be considered the time to sustained hospital discharge. Note for subjects with no missing data, the time to sustained discharge will be per the rules in Section 10.12. If a subject was re-hospitalized for a non-COVID-19 related reason, the subject will not be considered discharged during this re-hospitalization period for this analysis. For all subjects who do not have the event or who die, they will be censored at Day 60. The calculation will be as follows:

$$\text{Time to sustained discharge (Days)} = \text{Date of Event or Censor} - \text{Date of first dose of IMP} + 1$$

For subjects where the event occurs on an imputed visit, the value of time to sustained discharge will be set to the trial day of the imputed visit (i.e. if the event first occurs for Day 29 and is an imputed value, the time to sustained discharge will be set to 29). For each of the datasets the analysis (stratified log-rank) as per Section 12.5.3.2 will be implemented.

Number of Days Oxygen Free

A subject will be considered as oxygen free at a time point if the observed and imputed value of the adjusted 8-point ordinal scale is 1, 3 or 4. For each of the datasets imputed in step 2, the analysis as per Section 12.5.3.3 will be implemented.

Proportion of subjects free of respiratory failure at Day 8, 15, 22, 29, 60

A subject will be considered a responder at a time point if the value of the 8-point ordinal scale is ≤ 5 . For each of the datasets imputed in step 2, the analysis as per Section 12.5.3.4 will be implemented.

Subjects discharged and free of supplemental oxygen at Day 8, 15, 22 and 29

A subject will be considered a responder at a time point if the value of the adjusted 8-point ordinal scale, observed and imputed, is 1. For each of the datasets imputed in step 2, the analysis as specified in Section 12.5.3.5 will be implemented.

Number of Days Free of Respiratory failure

A subject will be considered free of respiratory failure at a time point if the value of the 8-point ordinal scale is ≤ 5 . For details on this derivation refer to Section 10.13. For each of the datasets imputed in step 2, the analysis as per Section 12.5.3.3 will be implemented.

Other Non-Key Secondary Endpoints

For the endpoints of proportion of subjects on invasive mechanical ventilation or ECMO at Days 8, 15, 22, 29 and 60, a subject will be considered on invasive mechanical ventilation or ECMO if the imputed value at the time point is ≥ 7 .

For the endpoint of proportion of subjects on non-invasive, invasive mechanical ventilation, ECMO or supplemental oxygen use at Days 8, 15, 22, 29 and 60, subjects will be considered on non-invasive, invasive mechanical ventilation, ECMO or supplemental use if they have an imputed or observed score of ≥ 5 at the time point.

For sensitivity analysis for the endpoint of duration of hospitalization, the duration of multiple hospitalizations, including re-hospitalizations due to COVID-19 and non-COVID-19 related reasons in the period will be summed together to derive the overall duration of hospitalization. For subjects with no missing data, duration of hospitalization will be calculated as per Section 10.15. For subjects with missing data following observed discharge date, no additional days will be added for

duration if the imputed values are ≤ 2 following this date, otherwise if subjects have a value of > 2 following last observed discharge, the number of days where the imputed values are > 2 will be added to the observed duration. For subjects with missing data with no observed discharge date, if the imputed values are ≤ 2 , then the subject will have the duration of hospitalization calculated as relative day of last value > 2 – start date of hospitalization +1. If the subject has multiple values > 2 following the first imputed discharge, the number of days where the imputed value is > 2 will be added to the duration. Note that Day 59 should be used in the calculation if imputed Day 29 is > 2 and imputed Day 60 ≤ 2 . If imputed Day 29 ≤ 2 and Day 60 > 2 only Day 60 will be counted as in hospital.. If a subject does not have the event across the imputed and observed data duration will be calculated as Day 60/study completion – date of initial hospitalization +1.

4. Results from the analysis (log-rank, logistic regression as per Appendix 2, statistics from the analysis for number of days oxygen free as per Section 12.5.3.3 and ANOVA) will be combined using Rubin's rule (Rubin, 1987). Estimates will be combined using PROC MIANALYZE in SAS. Rubin's rule assumes the estimates are asymptotically normally distributed.

Analysis of Proportions using Logistic Regression (Appendix 2)

Estimates from the logistic regression are transformed using the method outlined in Appendix 2. The standardized weighted differences, standard errors and the 95% CI based on the delta method (Ge et al, 2011) are approximately normal, no adjustment is required.

Analysis using Log-Rank

Estimates from log-rank are based on a chi-square distributed statistic and prior to combining the estimates via Rubin's rule, the estimates will need to be normalized using a Wilson-Hilferty transformation (Moscovici and Ratitch, 2017).

Analysis using Cox Regression

For results from Cox regression, the estimates obtained from PROC PHREG are log hazard ratios, and after combining via Rubin's rule, the results will be exponentiated to obtain the hazard ratios and associated confidence intervals (Moscovici and Ratitch, 2017).

ANOVA

Estimates from ANOVA are approximately normal and no transformation is required.

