8.1 Sample Size Considerations

The sample size is based on the all-cause mortality up to Day 60. For the placebo (SOC) group, the proportion of subjects dead at Day 60 is estimated to 10% (Marconi et al., 2021).

With 150 evaluable subjects per trial group, there will be an 80% power to detect a difference between C21 and placebo if the proportion of subjects dead at Day 60 in the C21 group is 2.5% (corresponding to a Hazard Ratio of 0.24). In this calculation a 5% withdrawal rate has been assumed. For the actual detection limit (corresponding to 50% power), if 15 subjects die in the placebo group, significance will be seen if at most 6 subjects die in the C21 group.

This assumes using a 2-sided test at a 5% significance level. Analysis will be by intention-to-treat; thus, all randomized subjects should be accounted for in the statistical evaluation.

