10.11 All-Cause Mortality

All-cause mortality is defined as time to day of death from any cause during the study. Time to all-cause mortality will be defined as:

$$\text{Time to all cause mortality (days)} = \text{Date of Death or Censor} - \text{Date of first dose of IMP} + 1$$

where the date of death will correspond to the date of death recorded in the CRF. Subjects without the event will be censored at day of withdrawal/Day 60 follow-up date in this analysis. If a subject is indicated to have died in the data, but date of death is missing, the last available date for the subject in the database will be used as the day of death.

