10.14 Number of Respiratory Failure Free Days

The number of days a subject is free of respiratory failure will be the number of days a subject has a score of ≤ 5 on the ordinal scale post-baseline.

If a subject dies, they will be considered in respiratory failure from the date of death up to Day 60.

For hospitalized subjects this will be the number of days a subject has a score of ≤ 5 on the 8-point ordinal scale CRF page. Up to Day 29, the adjusted 8-point ordinal scale will be used, for days between Day 29 and Day 60 the following rules will apply:

- If the clinical status on both days is ≥ 6 the subject will be assumed to be in respiratory failure for all days between Day 29 and Day 60.
- If the clinical status on both days is ≤ 5 and there is no observed data (for example unscheduled visits) indicating a worsening of status the subject will be assumed to be respiratory failure free for all days between Day 29 and Day 60. If there is a worsening of a status such that the ordinal scale has a value of ≥ 6 , the subject will not be considered respiratory failure free from the duration of this status (if duration of status is known).
- If the clinical status at Day 29 is ≥ 6 and Day 60 is ≤ 5 and the date of the change of status is known, the subject will be counted as respiratory failure free from the date the status improved. If the date of change in status is unknown (for example data is imputed), only Day 60 will be counted as respiratory failure free.
- If the clinical status at Day 29 is ≤ 5 and Day 60 is ≥ 6 and the date of the change of status is known, the subject will be counted as respiratory failure free until the date the status worsen. If the date of change in status is unknown (for example data is imputed), only Day 60 will be counted as in respiratory failure.

For discharge subjects, if a subject does not have a change in status up to Day 60 following discharge i.e. they are not re-hospitalized due to a COVID-19 related illness, the number of respiratory failure free days after discharge will be calculated as

$$\text{Respiratory Failure free (days)} = \text{Day 60 visit} - \text{Date of Discharge} + 1$$

If a subject is re-hospitalized due to a COVID-19 related illness and the ordinal scale on re-admission is ≥ 6 the number of respiratory failure free days after discharge and prior to re-hospitalized will be calculated as

$$\text{Respiratory Failure free (days)} = \text{Date of re-hospitalization} - \text{Date of Discharge}$$

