Appendix 5: Endpoint Derivation Details

Endpoint	Calculation	Handling of Death	Handling of Missing Data
All-Cause Mortality (Primary Analysis)	Date of event is the date of death Subjects without event will be censored at the time of completion/study discontinuation	n/a	n/a
All-Cause Mortality (Sensitivity Analysis including Multiple Imputation)	Proportion of deaths is the number of subjects with an ordinal scale value of 8 at Day 60	n/a	Missing data at Day 60 will be imputed.
Time to Sustained hospital discharge (Primary Analysis)	Date of event is the last date of discharge (for initial hospitalization or re-hospitalization for COVID-19 reasons) as recorded on the hospitalization form for subjects. If a subject has the event and subsequently withdraws (for reasons other than death) the subject will be treated as having the event If subject does not have event prior to completion/discontinuation the subject is censored at date of completion/discharge (for reasons other than death)	Subjects are treated as worst case (Day 60 is value used in analysis)	n/a
Time to Sustained hospital discharge (Sensitivity Analysis including Multiple Imputation)	Date of event is the last date of discharge (for initial hospitalization or re-hospitalization for any reason) as recorded on the hospitalization form for subjects with no missing data. For subjects with missing data, such that the event occurs at an imputed visit (≤ 2 ordinal scale occurs after which all subsequent visits stay at ≤ 2), time to sustained discharge will be the relative day of the imputed visit. For subject with Imputed data, if subjects discharges prior to missing data being observed and imputed values indicate the subject stays discharged (≤ 2), the last date of discharge recorded in the hospitalization form will be used For subjects with no event based on imputed and missing data, subjects will be censored at date of completion/Day 60.	Subjects are treated as worst case (Day 60 is value used in analysis)	Missing data will be multiple imputed
Number of days oxygen free up to Day 29	Sum of all ordinal scale values of 1, 3, 4 up to Day 29	Death treated as -1	Missing data will be multiple imputed

[figure not shown]
[figure not shown]

Endpoint	Calculation	Handling of Death	Handling of Missing Data

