Free of Respiratory Failure	Responder is defined as having an ordinal scale value of ≤ 5 at a visit	No special rules (death will be a non-responder as will have an ordinal scale value of 8)	Missing data will be multiply imputed
Subjects discharged from hospital and free of Supplemental Oxygen Use	Responder is defined as have a value of 1 on the adjusted ordinal scale at a visit	No special rules (death will be a non-responder as will have an ordinal scale value of 8)	Missing data will be multiply imputed
Subjects on Non-Invasive Mechanical Ventilation, Invasive Mechanical Ventilation, ECMO or with Supplemental Oxygen Use	Subjects with event has a score of ≥ 5 on the ordinal scale	No special rules (death will be a event as will have an ordinal scale value of 8)	Missing data will be multiply imputed
Subjects needing ICU stay	Subjects who have a record for ICU stay on the hospitalization CRF	Counted as in ICU from date of death	No
Subjects on Invasive or Mechanical Ventilation or ECMO	Subjects with event has a score of ≥ 7 on the ordinal scale	No special rules (death will be a event as will have an ordinal scale value of 8)	Missing data will be multiply imputed
Number of Respiratory Failure free days up to Day 60	Sum of all days where ordinal scale is ≤ 5 from Day 2 up to Day 29; Day 60. For days between Day 29 and Day 60 refer to Section 10.14.	Days from death treated as respiratory failure	Missing data will be multiply imputed
Duration of hospitalization	Duration: end date of hospitalization-start date of hospitalization +1 Sum all individual hospitalizations and re- hospitalization for COVID-19 together If a subject discontinues trial following discharge for reasons other than death, the duration will be calculated as normal and no additional days added If a subject discontinues prior to discharge 60 days will be used in the analysis	Subjects that die will be treated as in hospital from date of death	N

Endpoint	Calculation	Handling of Death	Handling of Missing Data

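### A death on a readout day can be classed as free of respiratory failure, and the SAP leaves open whether deaths after trial Day 60 count in the primary analysis

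*SAP*

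**What the plan says.** **Score on the day of death.** SAP 10.19.1 sets every day after the day of death to 8. It continues: "For the day of death, if the subject has a non-missing value on the ordinal scale that is not a value of 8", that value goes into the analysis. Only a missing score on that day becomes 8. Protocol 8.2.1 takes the daily score at the first assessment of the day. Under SAP 10.9, when a day has several scores, the one from the scheduled visit is used.

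**Deaths in the Day 15 and Day 29 endpoints.** Protocol 3 and 9.3.3, SAP 12.5.3.4 and 12.5.3.5 and Appendix 1 make failures only of subjects who die before Day 15. SAP 12.5.3.3 gives -1 oxygen-free days only to deaths before Day 29.

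**Other SAP text on deaths.** For respiratory failure free days, SAP 10.14 says of subjects who die that "they will be considered in respiratory failure from the date of death up to Day 60". For the proportion free of respiratory failure, Appendix 5 sees no need for a special rule because "death will be a non-responder as will have an ordinal scale value of 8". For oxygen-free days, Appendix 5 gives deaths -1 with no time limit.

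**Mortality.** SAP 10.11 states: "All-cause mortality is defined as time to day of death from any cause during the study". Subjects without the event are censored at withdrawal or at the Day 60 follow-up, a visit with a window of 3 days either side. For the imputation-based sensitivity analysis, Appendix 5 states: "Proportion of deaths is the number of subjects with an ordinal scale value of 8 at Day 60". SAP 12.5.2.3 describes that analysis as counting deaths up to and including Day 60.

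**The concern.** Two boundaries are not pinned down.

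1. **The readout day.** A rule that keeps the morning score can record a death as a success on a key secondary endpoint. The SAP's derivation table assumes this cannot happen. Two programmers could each follow the SAP and classify the same subject differently.

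2. **Trial Day 60.** The primary endpoint is mortality up to Day 60, but its derivation has no upper limit in trial days. About 19 deaths are planned for, so whether one late death is an event should not depend on which section is read.

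**Working it through.** **The plan's own figures first.** Inputs from SAP 8.1: 10% dead on placebo, 2.5% on C21, 150 per arm, two-sided 5%, 5% withdrawal, power stated as 80%.
- Hazard ratio: ln(0.975)/ln(0.90) = 0.240, as stated.
- Power: a log-rank simulation (4,000 runs, exponential death times, 5% withdrawal) gives 79.0%, close to the stated 80%.
- Expected deaths: 150 x (0.10 + 0.025) = 18.75.
- Detection limit, 15 vs 6: the pooled proportion is 21/300 = 0.07, the difference is 0.06, and z = 0.06/sqrt(0.07 x 0.93 x 2/150) = 2.04. This gives p=0.042, so the stated limit of at most 6 is reproduced.

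**Death on Day 15.** Take a subject scored 5 at the first assessment of Day 15 who dies that afternoon.
- SAP 10.19.1: the score is present and is not 8, so 5 is kept. An unscheduled 8 later that day would not displace the scheduled score (SAP 10.9).
- SAP 12.5.3.4: 5 or less is a responder, and the death rule does not apply because death was not before Day 15.
- SAP 10.19: worst-case handling starts after the date of death, so it does not apply either.
- Result: responder. Appendix 5 implies non-responder, and SAP 10.14 counts that same day as respiratory failure.

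The same path exists at Days 8, 22, 29 and 60. For discharged and oxygen-free at Day 15 it would need a score mapping to 1 on the day of death, which is unlikely. A death on Day 29 is also unclear for oxygen-free days (SAP 12.5.3.3 against Appendix 5).

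**Death on the Day 60 readout day.** SAP 10.19.2 follows 10.19.1 with listed exceptions, and none of them changes the day-of-death rule. A subject with a score other than 8 on that day is therefore not a death under Appendix 5, but is one under 12.5.2.3. The mortality tipping point in 10.19.3 inherits this.

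**Deaths on Days 61 to 63.**

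| Text | Upper limit for an event |
|---|---|
| SAP 10.11 | None stated (during the study) |
| SAP 12.5.2.2 | Day 60 follow-up visit, which may fall on Day 63 |
| SAP Appendix 5, primary analysis | None stated (censor at completion or discontinuation) |
| Protocol 3, SAP 12.5.2, SAP Appendix 1 | Day 60 |

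**Expected size.** Assume a constant hazard, which is not in the documents: S(d) = (1-q)^(d/60), with q = 0.10 or 0.025 and 150 per arm.

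| Days | Formula | Placebo | C21 | Total |
|---|---|---|---|---|
| 15 | 150 x [S(14)-S(15)] | 0.26 | 0.06 | about 0.3 |
| 60 | 150 x [S(59)-S(60)] | 0.24 | 0.06 | about 0.3 |
| 61 to 63 | 150 x [S(60)-S(63)] | 0.71 | 0.19 | at most about 0.9 |

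The last row is an upper bound because it assumes nobody has yet had the Day 60 visit. The Day 15 row counts all deaths that day, and only some would have been scored 5 or less.

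**Effect of one late death on the primary test** (uncorrected chi-square, 150 per arm, as an approximation to the log-rank test):
- Counting one C21 death after Day 60 moves 15 vs 6 (p=0.042) to 15 vs 7: z = 0.0533/sqrt(0.0733 x 0.9267 x 2/150) = 1.77, p=0.076.
- Counting one placebo death after Day 60 moves 14 vs 6 (p=0.064) to 15 vs 6 (p=0.042).

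The choice of text can matter in either direction.

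**The case against.** The strongest defence is that the Day 15 handling is deliberate. The score is defined as status at the first assessment of the day, and the protocol estimand, SAP 12.5.3.4, Appendix 1 and SAP 10.19 all make a failure only of death before the readout or worst-case only the time after it. SAP 10.19.1 agrees with them. This stands in part: scoring same-day deaths as 8 changes a stated estimand and is more than a typing correction. It does not remove the conflict with Appendix 5 or the mismatch with SAP 10.14.

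Rarity also counts. In the phase 2 trial all four deaths were in patients who needed mechanical ventilation (Protocol 2.2). Such patients would usually score 6 or 7 that morning and already be non-responders. The endpoint is fourth in the testing order and is exploratory unless the three tests above it succeed. The Day 60 case needs a score recorded on the day of death itself, although routine daily scoring ends at Day 29.

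A reader might infer three stronger things that the documents do not support:
- **That the day-of-death rule could tip the primary test.** It cannot. SAP 10.11 takes the date of death from the CRF, and the ordinal score plays no part in the log-rank test.
- **That a Day 60 death could be a survivor in the primary analysis.** Only the imputation-based sensitivity analysis and its tipping point are exposed.
- **That deaths on Days 61 to 63 do count.** The uncapped derivation text allows it, but the estimand and Appendix 1 would censor such a subject. The finding is an unresolved contradiction.

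**Conclusion.** The point holds as a minor correction. The rule in SAP 10.19.1 classes some readout-day deaths as responders, against Appendix 5 and out of line with SAP 10.14. In the mortality sensitivity analysis and its tipping point, it can class a death on the Day 60 readout day as a survivor, against 12.5.2.3. Separately, the SAP gives two incompatible upper limits for a primary event.

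Fewer than one death is expected at each boundary, given the planned mortality rates and the constant-hazard assumption. The p-values near the detection limit bear only on the Days 61 to 63 question, since only that one reaches the primary analysis. Planned sample size and power are unchanged, because the design already uses proportions dead at Day 60.

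**What to change.** - **SAP 10.19.1:** set the adjusted score to 8 on the day of death and every day after, whatever was recorded earlier that day.
- **Protocol 3 and 9.3.3, SAP 12.5.3.3 to 12.5.3.5, Appendices 1 and 5:** apply the death rules to deaths on or before Day 15, and on or before Day 29 for oxygen-free days.
- **SAP 10.19.2 and the matching row of Appendix 5:** count deaths by date of death on or before Day 60.
- **SAP 10.11, 12.5.2.2 and the primary-analysis row of Appendix 5:** count deaths with trial day 60 or less, and censor no later than trial Day 60.

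The cost is a few sentences spread over these sections, with no new data and no change to sample size. Because the Day 15 and Day 29 wording also stands in the protocol, the change needs a protocol edit or an entry in SAP 6.1, which already lists departures from the protocol. It should be settled before unblinding, since reclassifying a death afterwards would look post hoc.
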